### 1.3 Pseudoprogression can be difficult to differentiate from true tumor progression:

Following treatment with radiotherapy, inflammatory changes are often seen on MRI. Thus, strict criteria are used to categorize the nature of the tumor's response. The historical standard criteria were published by Macdonald et al. and required  $\geq 25\%$  increase in the sum of the products of perpendicular diameters of enhancing lesions, any new lesion, or clinical deterioration in order to declare progression.[11] These

criteria have come into question, as there can be significant interobserver variability, particularly in measuring irregularly shaped or cystic tumors. In addition, changes in contrast enhancement are typically nonspecific and simply represent a disrupted blood-brain barrier. Thus, fluctuations in contrast enhancement may be caused by inflammatory changes in the treated region, anti-angiogenic agents and radiation necrosis.[12] Pseudoprogression, defined as an increase in contrast enhancement that subsides without anti-neoplastic therapy, is common after standard treatment with radiotherapy and temozolomide.[13] This process is thought to be driven by radiation-induced increased permeability of the blood brain barrier. Because pseudoprogression typically occurs within 12 weeks of radiotherapy inside the high-dose region, the updated Response Assessment in Neuro-Oncology (RANO) criteria require new enhancement outside the 80% isodose line or viable tumor on histopathologic sampling for progression to be declared less than 12 weeks after radiotherapy.[14] These criteria help differentiate pseudoprogression from true progression, though challenges in interpreting changes in imaging after 12 weeks still remain.

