###### 11.412 Partial Response (PR): Requires all of the following:

- $\geq 50\%$  decrease compared to baseline in the sum of products of perpendicular diameters of all measurable enhancing lesions sustained for at least 4 weeks
- No progression of non-measurable disease
- No new lesions
- Stable or improved non-enhancing (T2/FLAIR) lesions on same or lower dose of corticosteroids compared to baseline scan
- The corticosteroid dose at the time of the scan evaluation should be no greater than the dose at time of the baseline scan
- Stable or improved clinically

11.413 Stable Disease (SD): Requires all of the following:

- Does not qualify for complete response, partial response, or progression
- Minimum 4 weeks duration
- Stable non-enhancing (T2/FLAIR) lesions on same or lower dose of corticosteroids compared to baseline scan. In the event that the corticosteroid dose has been increased, the last scan considered to show stable disease will be the scan obtained when the corticosteroid dose was equivalent to the baseline dose
- Stable clinically

11.414 Progression: Defined by any of the following:

- $\geq 25\%$  increase in the sum of products of perpendicular diameters of enhancing lesions compared to the smallest tumor measurement obtained either at baseline (if no decrease) or best response, on stable or increasing doses of corticosteroids
- Significant increase in T2/FLAIR non-enhancing lesion on stable or increasing doses of corticosteroids compared to baseline scan or best response following initiation of therapy, not due to co-morbid events (e.g. radiation therapy, demyelination, ischemic injury, infection, seizures, post-operative changes, or other treatment effects)
- Any new lesion
- Clear clinical deterioration not attributable to other causes apart from the tumor (e.g. seizures, medication side effects, complications of therapy, cerebrovascular events, infection, etc.) or changes in corticosteroid dose. The definition of clinical deterioration is left to the discretion of the investigator but it is recommended that a decrease in 20% of KPS or from any baseline to 50% or less be considered, unless attributable to co-morbid events.
- Failure to return for evaluation due to death or deteriorating condition
- Clear progression of non-measurable disease

11.415 Pseudoprogression (PsP): All of the following must be true:

- Progression of contrast enhancing lesions and or T2/FLAIR is restricted to the initial radiation therapy volume.

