## 11.416 Summary of the RANO Response Criteria Table

	CR	PR	SD	PD 	Preliminary PD/PsP 
T1-Gd +	None	≥50% decrease	<50% decrease- <25% increase	≥25% increase*	Any increase is restricted to initial RT Volume
T2/FLAIR	Stable or decrease	Stable or decrease	Stable or decrease	Increase*	Any increase is restricted to initial RT Volume
New Lesion	None	None	None	Present*	None
Corticosteroids	None	Stable or decrease	Stable or decrease	NA	Stable or decrease
Clinical Status	Stable or improved	Stable or improved	Stable or improved	Worsened*	Stable or improved
Requirement for Response	All	All	All	Any*	All

CR = complete response; PR = partial response; SD = stable disease; PD = progressive disease, PsP = Pseudoprogession

NA - Increase in corticosteroids alone will not be taken into account in determining progression in the absence of persistent clinical deterioration

1. RANO Progression occurs when any of the criteria with \* are present.
2. Confirmed PD requires all of the following If not all criteria are met then Preliminary PD
  - More than 3 months post RT
  - Radiologic progression by central review by RANO criteria
  - Clinical progression as determined by treating Oncologist
  - Cannot be considered Pseudoprogession
3. Patients with possible PsP should initially be given the Objective Status of Preliminary Progression. Once PsP or Progression is confirmed, the Objective Status can be changed accordingly. If Progressive Disease is subsequently confirmed, the Objective Status is to be recorded for the current cycle as PD (confirmed) and the back-dated date of the progressive disease (from the cycle with the initial Preliminary PD) is to be used as the date of progressive disease which is documented via the Event Monitoring Form. If progressive disease is not confirmed the Objective Status for the current cycle can be documented as SD, PR, or CR as appropriate using the baseline scan measurement as the baseline for comparison with the current measurement. The Objective Status for the cycle initially documented as Preliminary PD can be changed to PsP.

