## 11.417 Confirmatory Measurement/Duration of Response

11.4171

Confirmation:

To be assigned a status of PR or CR, changes in tumor measurements must be confirmed by repeat

assessments that should be performed 4 weeks  
after the criteria for response are first met.

11.4172

Duration of Overall Response:

The duration of overall response is measured from the time measurement criteria are met for CR or PR (whichever is first recorded) until the first date that recurrent or progressive disease is objectively documented (taking as reference for progressive disease the smallest measurements recorded since the treatment started). The duration of overall CR is measured from the time measurement criteria are first met for CR until the first date that recurrent disease is objectively documented.

11.4173

Duration of Stable Disease:

Stable disease is measured from the start of the treatment until the criteria for progression are met, taking as reference the smallest measurements recorded since the treatment started.

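### Footnote 3 of 11.416 re-classes an unconfirmed Preliminary PD against the baseline scan, while 11.413, 11.414 and 11.417 judge progression from the smallest measurement, so regrowth after shrinkage can be both SD and progression

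*Combined protocol and SAP*

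**What the plan says.** Four rules of the combined protocol and SAP meet at this point.

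- **Progression (11.414).** An increase of at least 25% in the sum of products, "compared to the smallest tumor measurement obtained either at baseline (if no decrease) or best response". For durations, 11.4172 and 11.4173 use the same kind of reference; 11.4173 has "taking as reference the smallest measurements recorded since the treatment started".
- **Stable disease (11.413).** The scan must meet this condition: "Does not qualify for complete response, partial response, or progression". The summary table in 11.416 gives the SD range as "<50% decrease- <25% increase" and names no reference scan.
- **Partial response (11.412).** At least a 50% "decrease compared to baseline in the sum of products of perpendicular diameters of all measurable enhancing lesions sustained for at least 4 weeks". Here baseline is the stated reference.
- **Preliminary PD (11.416, footnotes 2 and 3).** Footnote 2 confirms PD only if four conditions all hold: more than 3 months since RT, radiologic progression on central review, clinical progression, and not pseudoprogression. Under footnote 3, a PD confirmed later takes the date of the first Preliminary PD. If PD is not confirmed, the current scan may be given SD, PR or CR "as appropriate using the baseline scan measurement as the baseline for comparison with the current measurement", and the earlier call may be relabelled PsP.

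**The concern.** Baseline is the correct comparator for CR and PR. It is not the comparator that separates SD from progression anywhere else in Section 11. Once a lesion has shrunk, the two references diverge, and footnote 3 drops the nadir test at the moment it is needed: when someone must decide whether a suspected progression has gone away.

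An assessor who follows footnote 3 literally can record SD for a scan that 11.414 calls progression and that 11.413 therefore bars from SD. Two careful assessors could code the same patient differently, each with a section to cite. The baseline reference can only make regrowth look milder. Shrinkage followed by regrowth is also foreseeable: 7.6 recommends concurrent bevacizumab where possible, and 1.5 describes rapid falls in enhancement with VEGF-pathway inhibitors as relatively common.

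What is at stake is the date of progression. Time to progression (16.711) runs to the earliest documented progression, PD moves the patient to event monitoring (13.4), and the scan showing progression is the one contoured for patterns of failure (7.9, 16.83).

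**Working it through.** **1. The plan's own figures.** Section 16.2 states alpha 0.186 at a 20% success rate and power 85.9% at 40%. With X1 and X2 independent Bin(10, p), continuing if X1 ≥ 2 and positive if the total is ≥ 6, the probability of a positive trial is the sum over x = 2 to 10 of P(X1 = x) × P(X2 ≥ 6 − x). This gives 0.1863 and 0.8586, so both figures reproduce. Neither depends on the reference scan.

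**2. How far the two references diverge.** Let the nadir be f × baseline.

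- 11.414 calls progression from 1.25 × f × baseline.
- The table's SD range, read against baseline as footnote 3 directs, runs to just under 1.25 × baseline.
- Growth above nadir still allowed as SD is therefore 1.25/f − 1.

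| f | Progression under 11.414 from (× baseline) | SD ceiling under footnote 3 (× baseline) | Growth above nadir at that ceiling |
|---|---|---|---|
| 0.7 | 0.875 | 1.25 | 79% |
| 0.5 | 0.625 | 1.25 | 150% |
| 0.4 | 0.500 | 1.25 | 213% |

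If the lesion never shrank (f = 1), both rules give 25% and there is no conflict.

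**3. One patient through both rules.** Take a baseline sum of products of 1000 and a nadir of 400. An in-field rise to 600 is Preliminary PD (600/400 − 1 = +50% from nadir). The next scan is 650, and the patient is clinically stable.

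- Footnote 2: PD is not confirmed, because there is no clinical progression.
- Footnote 3: 650/1000 − 1 = −35% from baseline, hence SD.
- 11.414: 650/400 − 1 = +62.5% from nadir, hence progression, and 11.413 excludes SD.

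**4. Effect on the date.** If the status stays Preliminary PD, a later confirmation is dated to the 600 scan. If the 650 scan is recorded as SD, later growth may be treated as a new event and dated to its own first flag. If that flag comes at the scan after the 650 scan, the date moves by two scan intervals. At the typical 2–3 months in note 5 of Section 4.0, that is 2 × 2 = 4 to 2 × 3 = 6 months. This is an illustration, because actual timing is at the clinician's discretion.

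**5. Can it reach the 3-month endpoint?** Section 4.0 schedules MRI at 1 month ± 7 days and 3 months ± 14 days post RT. Assume RT spans about 11 days and starts 0–21 days after registration (the documents do not fix that gap), with 30 and 91 days for 1 and 3 months.

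- 1-month scan: earliest 0 + 11 + 30 − 7 = day 34; latest 21 + 11 + 30 + 7 = day 69.
- 3-month scan: earliest 0 + 11 + 91 − 14 = day 88; latest 21 + 11 + 91 + 14 = day 137.

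Shrinkage then regrowth needs two post-RT scans. If the 1-month scan is the first and shows growth, the smallest earlier measurement is baseline and the two references agree. On the registration clock of 16.21 (about day 91), the second scan is in time only at the early edge, or if unscheduled scans are done. If 3 months is counted after reirradiation, as 2.11 words it, the 3-month scan counts.

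**The case against.** **The footnote is permissive, and 11.413 still applies.** Footnote 3 says what may be recorded and leaves room for judgement. Read with 11.413, baseline could serve only the response comparison while the nadir test survives. This stands in part: the outcome is not forced. But the footnote names one comparator for all three categories and does not refer back to 11.413, so the plan permits two answers.

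**The tempting stronger reading.** A reader might infer that the baseline comparator turns failures into pseudoprogression, hence successes, and so inflates the chance of a positive trial. The documents do not support that, for these reasons:

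- The change to PsP follows from non-confirmation under footnote 2 and from 11.415. The latter asks for in-field change, no new enhancing lesion outside the RT volume and a clinically stable or improved patient. It has no size reference, so the patient in the example could be called PsP without the baseline phrase, as could one whose lesion never shrank.
- Section 1.3 describes pseudoprogression as "defined as an increase in contrast enhancement that subsides without anti-neoplastic therapy", but that is background. The operative definition in 11.415 does not require the lesion to subside.
- Section 16.21 does not mention PsP. Counting it as a success is inference.
- Applying the 30–35% response rate of 1.4 to 20 patients gives 6–7 responders, but that rate comes from bevacizumab trials. The 20% null rests on PFS after bevacizumab failure, and 7.6 does not require the drug. Responders are also not the same as patients who regrow in field, in time, and stay clinically stable.
- Moving one or two of 20 patients from failure to success (20% to 25% or 30%) would raise the chance of a positive trial from 18.6% to 36.7% or 56.4%. The one or two has no source, so these are what-if values only.

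**Timing.** On the registration clock the sequence rarely fits inside 3 months. This stands and limits the point.

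**Conclusion.** The contradiction is real and confined to SD versus progression in patients whose lesion first shrank. Footnote 3 allows SD at up to 79%, 150% or 213% above nadir for f = 0.7, 0.5 or 0.4, where 11.414 calls progression at 25%. These figures follow from the plan's own thresholds; the values of f are chosen for illustration.

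The main consequence is a possible loss of the back-dated progression date, with longer time to progression and an effect on durations of response and of SD and on which scan is taken as showing progression. An effect on the 3-month primary endpoint is limited to the post-reirradiation reading in 2.11 or to early or unscheduled scans. It rests on the assumed 11 days of RT and 0–21 days from registration to its start. No reclassification rate, and so no bias in the success proportion, can be derived from the documents.

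**What to change.** In footnote 3, keep the baseline scan as the reference for CR and PR. Add that SD also requires the current measurement to be less than 25% above the smallest measurement since treatment began, in line with 11.413 and 11.414. If that fails, the status stays Preliminary PD, so that a later confirmed progression keeps its back-dated date.

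Do not add a nadir condition to the PsP label. It would conflict with 11.415, which has no size criterion.

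The cost is one sentence and no new data. Some slowly resolving pseudoprogressions will stay Preliminary PD for longer.

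Two matters stay open. With a nadir below 0.4 of baseline, a regrown lesion can still be at least 50% below baseline and also 25% above nadir; that overlap lies between 11.412 and 11.414 themselves. And 16.21 does not say how a patient still in Preliminary PD at 3 months is counted.

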## 11.417 Confirmatory Measurement/Duration of Response

11.4171

Confirmation:

To be assigned a status of PR or CR, changes in tumor measurements must be confirmed by repeat

assessments that should be performed 4 weeks  
after the criteria for response are first met.

11.4172

Duration of Overall Response:

The duration of overall response is measured from the time measurement criteria are met for CR or PR (whichever is first recorded) until the first date that recurrent or progressive disease is objectively documented (taking as reference for progressive disease the smallest measurements recorded since the treatment started). The duration of overall CR is measured from the time measurement criteria are first met for CR until the first date that recurrent disease is objectively documented.

11.4173

Duration of Stable Disease:

Stable disease is measured from the start of the treatment until the criteria for progression are met, taking as reference the smallest measurements recorded since the treatment started.

**12.0 Descriptive Factors**

- Corticosteroid therapy at study entry: yes (specify dose) vs no
- Histologic grade of primary tumor: 3 vs 4
- Histologic type of primary tumor: oligodendroglioma vs oligoastrocytoma vs astrocytoma vs other (specify)
- ECOG PS (see Appendix I): 0 vs 1 vs 2 vs 3
- Neurologic deficit: yes (specify) vs no
- History of seizures: yes (specify last seizure) vs no
- Prior surgical resection or biopsy: yes vs no
- Age:  $\leq 70$  vs  $> 70$
- MGMT: methylated vs unmethylated vs not available
- IDH status: mutated vs wild type vs not available
- 1p/19q status: single deleted vs codeleted vs not available
- Time since last RT course:  $< 6$  months vs 6-12 months vs  $> 12$  months
- Salvage chemotherapy: yes (specify agents, dates treated) vs no

### 13.0 Treatment/Follow-up Decision at Evaluation of Patient

- 13.1 A patient is deemed *ineligible* if after registration, it is determined that at the time of registration, the patient did not satisfy each and every eligibility criteria for study entry. The patient will go off study.
- If the patient received MR and PET for radiotherapy planning, all data up until the point of confirmation of ineligibility must be submitted.
  - If the patient never received pre-RT PET, on-study material must be submitted. No additional follow up is necessary.
- 13.2 Those patients who will not receive any radiation treatment or who will receive radiation treatment elsewhere (not at Mayo Clinic) will be considered non-evaluable for the study endpoint and move to Event Monitoring phase per Section 18.0.
- 13.3 Patients who are CR, PR, REGR, or SD will continue to obtain MRI scans at each clinically indicated follow-up for up to 2 years from registration.
- 13.4 Patients who develop PD or withdraw from further follow-up scans will go to the event-monitoring phase per Section 18.0.

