#### 3.2 Exclusion Criteria

- 3.21 More than one prior course of radiotherapy or prior prescription doses exceeding 60 Gy to re-irradiation target volumes
- 3.22 Unable to undergo MRI scans with contrast
- 3.23 Unable to undergo an  $^{18}\text{F}$ -DOPA-PET scan (e.g., Parkinson's Disease, taking anti dopaminergic, or dopamine agonist medication or less than 6 half-lives from discontinuance of dopamine agonists.)

Note: Other potentially interfering drugs: amoxapine, amphetamine, benztropine, bupropion, buspirone, cocaine, mazindol, methamphetamine, methylphenidate, norephedrine, phentermine, phenylpropanolamine, selegiline, paroxetine, citalopram, and sertraline). If a patient is on any of these drugs, list which ones on the On-Study form.

- 3.24 Any of the following:
  - Pregnant women
  - Nursing women
  - Men or women of childbearing potential who are unwilling to employ adequate contraception

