10.9 Reporting of Serious Adverse Events and Unanticipated Problems

When an adverse event has been identified, the study team will take appropriate action necessary to protect the study participant and then complete the Study Adverse Event Worksheet and log. The investigator will evaluate the event and determine the necessary follow-up and reporting required.

10.91 Serious Adverse Events will be reported as part of regular adverse event reporting mechanisms via the data capture system and logged for review reporting.

10.10 Radiation Therapy adverse events to be graded at each evaluation and pretreatment symptoms/conditions to be evaluated at baseline per CTCAE v4.0 grading unless otherwise stated in the table below:

System Organ Class (SOC)	Adverse event/Symptoms	Baseline	During Treatment	Active Monitoring
General disorders and administration site conditions	Fatigue	X		X
Immune system disorders	Allergic reaction		X	
Nervous system disorders	Central nervous system necrosis			X
Nervous system disorders	Vasovagal reaction		X	
Injury poisoning and procedural complications	Bruising	X	X	
Skin and subcutaneous tissue disorders	Rash maculo-papular	X	X	

10.101 Submit via appropriate *reporting mechanisms (i.e., paper or electronic)* the following AEs experienced by a patient.

10.1011 Grade 2 AEs deemed possibly, probably, or definitely related to the Radiation Therapy

10.1012 Grade 3 and 4 AEs regardless of attribution to Radiation Therapy

10.1013 Grade 5 AEs (Death)

10.1014 Any death within 30 days of the patient's last treatment or procedure regardless of attribution to the study treatment or procedure

10.1015 Any death more than 30 days after the patients last study treatment or procedure that is felt to be at least possibly treatment related must also be submitted as a Grade 5 AE, with a CTCAE type and attribution assigned.

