##### 16.71 Primary Endpoint:

16.711 Definition: the primary endpoint of this trial is proportion of patients experiencing progression-free survival at 3 months. All patients meeting eligibility criteria who have a signed consent form on record and who have begun F-DOPA-guided reirradiation treatment at Mayo Clinic will be evaluable for the endpoint. All eligible patients will be followed until death or a maximum of 4 years. Time to disease progression is defined as the time from study registration to the earliest date documenting disease progression. If a patient dies without evidence of disease

progression, the patient will be censored on the last date the tumor was evaluated. If a patient is declared to be a major treatment violation, the patient will be censored on the date the treatment violation was declared to have occurred. In the case of a patient starting treatment and then never returning for any evaluation, the patient will be censored for progression on the last day of therapy.

16.712 Estimation: the proportion of successes will be estimated by the number of successes divided by the total number of evaluable patients. Confidence intervals for the true success proportion will be calculated according to the approach of Duffy and Santner.[37]

16.713 Over Accrual: if more than the target number of patients are accrued, the additional patients will not be used for evaluation of stopping rules or in any decision making process. They will be included in the final point estimates and confidence limits.

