Using the radiation treatment dosing, fractionation and normal tissue constraints outlined in Section 7 have been performed in several studies without significant adverse effects. While radiation-induced brain necrosis is rare, a cumulative normal brain dose of < 100 Gy in 2 Gy equivalents has been suggested as a constraint to minimize the risk of necrosis.[30] Two large studies reported no grade 3 or higher toxicity and no radionecrosis using the same dosing and fractionation as our protocol.[26, 27] In fact, studies using larger fraction sizes (5 Gy/fraction) reported very low rates of radionecrosis when keeping reirradiation doses under 40 Gy.[28, 29] However, tumor progression is expected in the majority of patients and commonly results in severe neurologic symptoms near the end of life. Both acute (available at <http://ctep.cancer.gov>) and late [39] toxicity will be monitored continuously as each patient is accrued and follow-up data are accumulated. If at any time, 1) 3 or more of the first 9 AE-evaluable patients; or, 2) after 10 or more patients are AE-evaluable, more than 30% experience any of the following adverse effects considered to be at least possibly related to radiation treatment up to and including the three-month timepoint; enrollment will be suspended so the details of each episode may be examined and a trial recommendation will be formulated and presented to the MCCC DSMB, adjusting the dose, fraction size or volumes as needed.

- Grade 3 or 4 irreversible CNS toxicity
- Grade 4 non-hematologic, non-CNS toxicity
- Any Grade 5 toxicity

Initial estimated Primary Completion Date: At study activation, this study will have been registered within the www.ClinicTrials.gov (CT.gov) website. The Primary and Secondary endpoints along with other required information for this study will be reported on CT.gov. For purposes of timing of the CT.gov results reporting, the initial estimated completion date of the primary endpoint of this study is 27 months after the study opens to accrual.

16.101 Definition of Primary-Endpoint Completion Date (PCD): The PCD is the date at which the last progression free patient has been followed for 3 months.

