#### Follow-up Material(s)

CRF	Event Monitoring Phase 		
	Yearly for 2 years	At PD	Death
Adverse Events: Late Toxicities	X	X	
Patient Status: Survival Status Follow-up/ Event Monitoring	X	X	X

1. If a patient is still alive 2 years after registration, no further follow-up is required.

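### Section 13.1 has no branch for a patient found ineligible after protocol reirradiation has begun, so scheduled toxicity and survival collection stops for someone already exposed

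*Combined protocol and SAP*

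**What the plan says.** Section 13.1 covers any patient who, after registration, proves not to have met every eligibility criterion: "The patient will go off study". Two sub-rules follow. One is for patients who had planning imaging: "If the patient received MR and PET for radiotherapy planning, all data up until the point of confirmation of ineligibility must be submitted". The other is for patients who never had the pre-RT PET; they owe on-study material only, and it says outright that no more follow-up is needed. Neither sub-rule mentions a patient who has received radiation.

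Section 13.2 deals with patients who get no radiation, or get it elsewhere. They "will be considered non-evaluable for the study endpoint and move to Event Monitoring phase per Section 18.0". Under Section 18.1 that phase collects late toxicity yearly for 2 years and at progression, and survival status at those times and at death.

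Section 16.711 ties long-term follow-up to eligibility: "All eligible patients will be followed until death or a maximum of 4 years".

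On safety, 16.91 says that acute and late "toxicity will be monitored continuously as each patient is accrued and follow-up data are accumulated". Its radiation rule counts qualifying events among AE-evaluable patients up to the three-month timepoint. The documents do not define AE-evaluable. Section 10.101 lists what must be submitted, with no eligibility condition: Grade 3 and 4 events whatever their cause (10.1012), Grade 5 events (10.1013), deaths within 30 days (10.1014), and "Any death more than 30 days after the patients last study treatment or procedure that is felt to be at least possibly treatment related" (10.1015).

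**The concern.** Eligibility is a reasonable condition for the efficacy analysis. It is a poor condition for safety follow-up, because the risk comes from exposure. Under 13.1, the discovery of an eligibility failure ends scheduled observation of a patient who has already been reirradiated.

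One route to ineligibility bears directly on that risk. Exclusion 3.21 reads "More than one prior course of radiotherapy or prior prescription doses exceeding 60 Gy to re-irradiation target volumes", and the brain constraints in 7.54 assume a prior dose of 60 Gy in 30 fractions. A patient who breaches 3.21 may fall outside that assumption. Toxicity and reoperation rates are secondary goals (2.22, 16.84, 16.85), and the 16.91 rule can suspend enrolment on very few events. A small loss of observed events therefore matters more here than in a large trial.

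**Working it through.** **1. Who is followed after leaving the main path**

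| Patient | Rule | Scheduled collection afterwards |
|---|---|---|
| Eligible, no protocol RT | 13.2 | Event Monitoring: late toxicity and survival |
| Ineligible, no PET | 13.1 | None, stated outright |
| Ineligible, MR and PET done, no RT | 13.1 | None assigned; data to confirmation only |
| Ineligible, protocol RT given | 13.1 (same sub-rule) | None assigned; data to confirmation only |

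The last two rows share one rule although only one group was irradiated. For them, the end of collection follows from off-study status together with the data cut-off; it is not stated separately. In the table of radiation adverse events in 10.10, CNS necrosis is graded only in the Active Monitoring column. A patient who leaves study before that phase has no scheduled necrosis grading. Section 10.11 also exempts necrosis of Grade 3 or below from expedited reporting.

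**2. What is lost, by date of confirmation**

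- Before the three-month timepoint: events between confirmation and that timepoint can be missed by the 16.91 rule, and everything later is uncollected.
- After the three-month timepoint: the 16.91 rule loses nothing. Late-toxicity, reoperation and survival data are lost.

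**3. The 7.54 figure**

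With α/β = 2, NTD = D(d + 2)/(2 + 2). For 31 Gy in 10 fractions, d = 3.1 Gy and NTD = 31 × 5.1/4 = 39.525 Gy. Adding the prior 60 Gy gives 99.525 Gy. The plan states 99.5 Gy, so its figure reproduces. The margin to the 100 Gy limit is 100 − 99.525 = 0.475 Gy, so the calculation depends closely on the prior dose that 3.21 is meant to cap.

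**4. Sensitivity of the 16.91 radiation rule**

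The rule suspends at 3 or more events in the first 9 AE-evaluable patients, and above 30% from the tenth. From 10 to 13 patients that means 4 events; from 20 to 22 it means 7. Take 3 events in the first 9, which suspends. If one event patient stays in the denominator with the event unseen, the count is 2 of 9, with no suspension. If that patient is dropped, it is 2 of 8, again with no suspension.

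**5. Illustration with assumed toxicity rates**

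The documents give no rates, so these are assumptions: 22 treated patients, 2 of them ineligible, independent events, and all events in the 2 occurring after confirmation (the extreme case). Let q_n be patient n's visible event probability. Then P_n(k) = P_{n−1}(k)(1 − q_n) + P_{n−1}(k−1)q_n, with probability moved to suspended as soon as a limit is met. Results are averaged over all positions of the 2 patients among the 22.

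| Rate, eligible / ineligible | All followed | Events unseen, kept in denominator | Dropped |
|---|---|---|---|
| 10% / 30% | 10.2% | 5.1% | 6.6% |
| 20% / 20% | 36.4% | 29.6% | 35.6% |
| 20% / 40% | 43.3% | 29.6% | 35.6% |
| 20% / 60% | 50.3% | 29.6% | 35.6% |

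Where the ineligible carry extra risk, the chance of suspension falls by between 10.2 − 6.6 = 3.6 and 50.3 − 29.6 = 20.7 percentage points. Without extra risk, dropping them costs 36.4 − 35.6 = 0.8 points. Leaving them in the denominator unobserved costs 36.4 − 29.6 = 6.8 points.

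**The case against.** The strongest reply is that the reporting duties in 10.101 carry no eligibility condition and already cover every grade that the 16.91 radiation rule counts. The exemptions in 10.11 concern expedited reports only, and 10.12 separately requires expedited reporting of possibly related deaths after 30 days. Data up to confirmation must also be submitted. This stands as a partial safeguard. A reader might infer that 13.1 contradicts 10.1014 and 10.1015, but the documents do not go that far: the duty exists, and what is missing is a visit or form through which a non-fatal event would be found.

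Other stronger readings also fail:

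- A reader might infer that late necrosis escapes the suspension rule because of 13.1. That rule stops at the three-month timepoint for every patient, so later necrosis never enters it.
- A reader might infer that untreated patients in general are followed better than treated ones. An untreated patient who is also ineligible goes off study too; the contrast holds only for eligible untreated patients.
- A reader might infer that ineligible patients are barred from the 16.91 count. Eligibility is a stated condition for the primary endpoint (16.711). In 16.91 exclusion is only a possible reading of an undefined term.
- A reader might extend the one-event argument to 4 of 10 becoming 3 of 9 when a patient is dropped. Three events in the first 9 still suspends.

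Frequency is also a fair objection. Eligibility is verified before registration (6.13), and planning depends on prior dose (7.54, 7.55), so a 3.21 breach would plausibly surface before treatment.

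**Conclusion.** The gap is real and structural. Section 13.1 gives no follow-up to a patient who was irradiated on protocol and then found ineligible, and neither 16.711 nor 16.91 clearly brings that patient back in. Adverse event duties survive on paper without scheduled collection behind them.

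The effect is bounded. Only events after confirmation are exposed, and the suspension rule is affected only when confirmation precedes the three-month timepoint. Within that window one unseen event can decide the rule, as 3 of 9 against 2 of 9 or 2 of 8 shows. The 3.6 to 20.7 point range rests on assumed rates, on both ineligible patients being treated, and on all their events being missed; it illustrates the effect and does not forecast it.

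A reader might take 2/22 = 9.1% as the ineligibility rate, or conclude that the highest-risk patients are routinely lost. Neither is supported. The allowance in 16.3 covers ineligibility, cancellation, major violation and other reasons together, and the higher-risk argument applies to breaches of 3.21, not to every eligibility failure. The point justifies a short amendment because the remedy is cheap and the data cannot be recovered later on a schedule that was never set.

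**What to change.** In 13.1, add a branch for an ineligible patient who has started protocol RT. Exclude that patient from the primary efficacy set only, continue the Section 4.0 adverse event assessments through 3 months post RT, then move the patient to Event Monitoring for late toxicity and survival. Say that reoperation is to be recorded as well, since Section 18.1 names no form for it. Reserve off-study status for ineligible patients who received neither tracer nor RT.

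In 16.91, define AE-evaluable by exposure, whatever the eligibility status: tracer received for the tracer rule, any protocol RT fraction for the radiation rule.

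The cost is a few sentences and follow-up forms for perhaps one or two patients. The safety set will differ slightly from the efficacy set, so reports must label the two. The primary endpoint definition and the treatment rules do not change.
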